At randomization, patients will receive study medication and instructions for its administration. Thereafter, patients will return to the clinic at 1, 6, and 12 months and then every 6 months until the end of study (efficacy cut-off date) is announced. At 3 months, the patient will be contacted by telephone. Throughout the study and at clinic visits, patients will be assessed for efficacy (stroke, systemic embolism, MI, CV death, or all-cause mortality) and safety (vital signs, bleeding, serious adverse events [SAEs] which are not outcome events, non-serious adverse events [AEs] leading to permanent discontinuation of study treatment, and any non-serious AEs of particular concern to the investigator).

The trial will continue until approximately 450 patients are anticipated to have experienced a positively adjudicated primary efficacy outcome event. This is anticipated to occur approximately 3 years after the first patient is randomized, but may vary depending on the recruitment rate as well as the primary event rate. A telephone safety visit will be performed 1 month after the end-of-treatment (EOT) visit.

Patients permanently discontinuing study treatment will continue to be followed, and outcome events and vital status must be assessed in these patients until the end of the study via either clinic visits or telephone contacts.

All efficacy and safety analyses are based on time from randomization to time of first event. Suspected clinical study outcomes will be assessed by the ICAC, which will be blinded to treatment allocation. Adjudicated results will be the basis for the final analyses. The IDMC will monitor patient safety during the study and give recommendations to the SC and sponsor.

A schematic of the study design is provided in [Figure 4–1](#).

[figure not shown]

Figure 4–1: Study design schematic - amended

¹⁰ Paragraph revised with global Protocol Amendment 5. See Section 13.1 for details.

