5.2 Discontinuation of patients from study treatment - amended

An excessive rate of patient discontinuations from either treatment or “drop-outs” from the study may render the trial non-interpretable. In this study, outcome events and vital status data are crucial to the primary analysis and must be collected until the end of the study, even if patients are no longer taking study medication. **Therefore, all efforts will be taken to**

¹⁹ Criterion revised with global Protocol Amendment 5. See Section 13.1 for details.

motivate patients to comply with all study procedures and to continue to be followed until the end of the trial.

Patients may discontinue study medication at their own request and without giving reasons (even though providing a reason is encouraged), based on the investigator's judgment, if the patient is pregnant, or at the request of the sponsor (exceptional circumstances). In case a patient is diagnosed with atrial fibrillation with an episode of at least 6 minutes during the study trial medication must be stopped (see section 6.9.2).²⁰ **Study drug will not be routinely discontinued in participants reaching a potential outcome event unless there is a safety concern or a clear indication for an alternative antithrombotic therapy as determined by the local investigator.**

In case of a temporary study medication interruption²¹ for any reason, study medication will be restarted as soon as medically justified in the opinion of the investigator. There is no defined maximum limit for temporary treatment interruption.

For all patients who permanently discontinue study medication, the patients will still be part of the study, and outcome events and vital status must be reported until the efficacy cut-off date for the study is announced. All safety data will continue to be collected for 1 month after the last study medication intake (safety follow-up visit). The investigator and patient must discuss and determine further follow-up options. Options for follow-up are listed below, in descending order of preference:

1. Patient continues the regular study clinic visits at the investigator's site as outlined in the protocol
2. Patient will be contacted by phone at the regular follow-up intervals
3. Patient allows his/her general practitioner or a family relative to be contacted (if allowed in respective country) at the regular follow-up interval
4. Patient will be contacted once at the end of the study

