7.5.1 Primary safety variable - amended

The primary safety variable is the time from randomization to time of first occurrence of a major bleeding defined as a bleeding event that meets at least one of the following criteria:

- Fatal bleeding, and/or
- Symptomatic³⁶ bleeding in a critical area or organ (intracranial, intraocular, intraspinal, pericardial, retroperitoneal, intraarticular, or intramuscular with compartment syndrome), and/or
- Clinically overt bleeding associated with a recent decrease in the hemoglobin level of ≥ 2 g/dL³⁷ (20 g/L; 1.24 mmol/L) compared to the most recent hemoglobin value available before the event, and/or
- Clinically overt bleeding leading to transfusion of 2 or more units of packed red blood cells or whole blood

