7.5.3.2 Adverse event reporting - amended

The safety observation period extends from the time the signed informed consent is obtained through the completion of the final study visit, 1 month post the EOT visit. In case

of permanent discontinuation of study medication, AEs other than outcome events must be reported up to 1 month after the last dose of study medication intake (Safety Visit).

All SAEs, all non-serious AEs leading to permanent discontinuation of study-drug treatment, and any non-serious AEs of particular concern to the investigator will be captured in the eCRF. Other non-serious AEs will not be collected due to the large available safety database for rivaroxaban.

The following detailed rules apply to AE and SAE handling:

- SAEs which are primary or secondary efficacy outcomes or appear indicative of an outcome event, e.g., TIA, MI or cardiac chest pain requiring hospitalization will be captured on an Outcome/CV Event page of the eCRF.
- All fatal events which are not considered cardiovascular deaths will be captured as outcomes (Death eCRF) but will also be reported to the sponsor's Pharmacovigilance (PV) Department in an expedited manner.
- All bleeding events including fatal bleeding will be captured in the eCRF (Bleeding page). Serious adverse events which are bleeding terms will not be reported to the sponsor's PV Department in an expedited manner. Symptomatic intracerebral /intraparenchymal hemorrhages as well as symptomatic subarachnoid hemorrhages will be captured as bleeding and as stroke. All subdural/epidural hematoma and asymptomatic intracranial bleeding are only reported as bleeding.³⁸
- All other events (including complications of efficacy or safety outcome events) that fulfill the seriousness criteria will be reported as SAEs in an expedited manner.
- All pregnancies in female study patients or in female partners of a male study patient will be reported as Pregnancy reports in an expedited manner.
- Non-serious AEs that have led to permanent study-drug discontinuation will be recorded on the AE page of the eCRF.
- Non-serious AEs which the investigator considers of particular concern will be recorded on the AE page of the eCRF. These may include events that are unexpected and/or reveal a pattern that is suggestive of a possible causal association or other non-serious events significant enough as to prompt the investigator to bring them to the attention of the sponsor.

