## **6.4 Safety**

### **6.4.1 Adverse events - amended**

Adverse events (AEs) will be coded by MedDRA. The version number of MedDRA used for the analyses will be stored in the clinical database/system set-up. A listing will be provided linking the original investigator terms and the coded terms.

Analyses of reported adverse events will be performed based on the safety analysis set.

In case of uncertainty (e.g., missing or incomplete dates), adverse events will be classified as “treatment emergent” following the worst case approach.

An overall summary of SAEs and treatment-emergent (TE) AEs will be generated by treatment group and overall.

Incidences of subjects with TEAEs, drug-related and/or serious TEAEs, TEAEs causing discontinuation of study drug, and TEAEs of particular concern will be summarized by treatment group and overall grouped by MedDRA Primary System Organ Class (SOC) and Preferred Term (PT). In addition, the incidence of pre-treatment AEs and AEs during the follow-up will be tabulated.

Serious adverse events (SAEs), AEs leading to discontinuation and AEs of particular concern will be listed. The date, relative day (to study medication) and phase of the study (pre-treatment, during treatment, post-treatment) will be included.

Further summaries of SAEs by intensity and outcome will be provided, consistent with Bayer Global Medical Standards.

Adverse events matching the SMQ Haemorrhage terms (excl laboratory terms) will be excluded from the AE analysis to avoid double counting of events. This is affecting data from Japan where bleeding events are additionally reported as AEs. In general bleeding events are reported separately and analyzed as described in the following sections.

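### Non-bleeding adverse events are tabulated by arm only as crude percentages, although their collection ends 1 month after the last dose; if drug stops differ by arm, the percentages mislead

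*Protocol*

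**What the plan says.** Protocol 4.1 states, and SAP section 3 repeats, "All efficacy and safety analyses are based on time from randomization to time of first event".

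The adverse-event plan is in SAP 6.4.1. It sets the population: "Analyses of reported adverse events will be performed based on the safety analysis set". It sets the measure: "Incidences of subjects with TEAEs, drug-related and/or serious TEAEs, TEAEs causing discontinuation of study drug", together with events of particular concern, summarised by arm and by MedDRA class and term. Events outside the treatment period are handled separately: "In addition, the incidence of pre-treatment AEs and AEs during the follow-up will be tabulated". Bleeding terms are taken out: "Adverse events matching the SMQ Haemorrhage terms (excl laboratory terms) will be excluded from the AE analysis to avoid double counting of events". The section names no person-time rate, no time-to-event method and no test. It also does not say how many days after the last dose still count as treatment-emergent.

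Two collection rules apply after a permanent drug stop:

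- Protocol 7.5.3.2: "AEs other than outcome events must be reported up to 1 month after the last dose of study medication intake".
- Protocol 5.2: "outcome events and vital status must be reported until the efficacy cut-off date for the study is announced".

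The formal safety variables are bleeding outcomes. Protocol 7.5.1 begins: "The primary safety variable is the time from randomization to time of first occurrence of a major bleeding". SAP 6.4.5 analyses them primarily in the ITT set with the ITT data scope.

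**The concern.** For adverse events that are neither bleeding nor outcome events, a patient who stops drug after 2 months is observed for about 3 months, and one who stays on drug for 2 years is observed for about 25. A crude proportion counts both as one subject in the denominator. The length of observation is decided after randomisation and may depend on treatment.

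If one arm loses more patients from study drug, its percentages fall because there was less time to see events. A reader comparing the columns could take that for better tolerability.

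Bleeding could produce such a difference. SAP section 1 reports more ISTH major bleeding on rivaroxaban, and Protocol 6.9.5 lists discontinuing study drug among the measures after serious bleeding. A patient who stops for bleeding adds nothing to the adverse-event tables for that event, because haemorrhage terms are excluded, but loses the later observation time. This makes unequal stops plausible. The documents do not say that they occurred.

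**Working it through.** The documents give no adverse-event rate, so there is no planned figure to reproduce on this point. The check asks what crude incidence shows when the true rates are equal.

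**Inputs from the documents**
- Permanent stops: 10% in year 1, 7% in following years, with no arm difference given (Protocol 8.6, SAP 4.6).
- Deaths 3% and loss to follow-up 1% per year (same sections).
- Recruitment 2 years, total duration 3 years (SAP 4.6). Planned follow-up is therefore taken as uniform between 1 and 3 years.
- Collection to 1 month after the last dose (Protocol 7.5.3.2).

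**Assumptions not in the documents**
- Constant hazard λ of a first adverse event, equal in both arms: 0.05, 0.10 or 0.20 per year.
- Stops in one arm at 1, 1.5 or 2 times the planned rates, unrelated to adverse-event risk.

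**Formulas**
- Write u = max(t − 1/12, 0), with stop proportions a in year 1 and b in each later year.
- Still on drug: S_D(u) = (1 − a)^u for u < 1, then (1 − a)(1 − b)^(u − 1).
- Still in planned follow-up: S_F(u) = 1 for u < 1, then (3 − u)/2 up to 3 years.
- Death or loss: c = −ln(0.97) − ln(0.99) = 0.0405 per year.
- Patient-years at risk per patient: PY = ∫ S_D(u) · S_F(u) · exp(−(λ + c)t) dt, from 0 to 3 + 1/12.
- Crude incidence = λ × PY. Rate = crude incidence / PY = λ.

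**Results at λ = 0.10**

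| Stops (year 1 / later) | PY per patient | Crude incidence | Ratio to planned stops | Rate ratio |
|---|---|---|---|---|
| 10% / 7% (planned) | 1.633 | 16.3% | 1.00 | 1.00 |
| 15% / 10.5% (×1.5) | 1.557 | 15.6% | 0.95 | 1.00 |
| 20% / 14% (×2) | 1.482 | 14.8% | 0.91 | 1.00 |

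For example, 0.10 × 1.482 = 0.148, and 0.148 / 0.163 = 0.91. Over λ from 0.05 to 0.20 the crude ratio is 0.95 to 0.96 at ×1.5 and 0.91 at ×2. The mean collection window, before counting first events, falls from 1.81 years to 1.72 and 1.64 years.

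Seen the other way, a true hazard ratio of about 1.05 to 1.06 (×1.5) or 1.11 to 1.12 (×2) against the arm with more stops would appear as equal percentages.

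**Check on the remedy.** The rate is exactly right here because the hazard is constant. Assume instead a front-loaded hazard of 20 per 100 patient-years for 6 months and 6.7 afterwards, a 2-year horizon without death or loss, and stops of 20%/15% against 10%/7%. The crude incidences are then 16.0% and 17.1%, a ratio of 0.94. The rates are 0.1599/1.476 = 0.108 and 0.1708/1.622 = 0.105, a ratio of 1.03. The distortion is about 3% instead of 6%, and in the opposite direction.

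**The case against.** Several points on the other side stand and limit the concern:

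- **Wording of 4.1.** A reader might infer that SAP 6.4.1 contradicts the protocol. In context the sentence sits beside outcome follow-up and adjudication. Protocol 7.5 identifies the safety outcomes as bleeding, and Protocol 8.3 defines the safety variables only by reference to 7.5.1 and 7.5.2. Taken literally, the sentence would also demand a time-to-event analysis of vital signs. It is loose wording and does not show that the SAP departed from the protocol.
- **Descriptive tables.** No between-arm test or effect estimate is planned for adverse events.
- **What the tables omit.** Stroke, systemic embolism, MI, cardiovascular death and bleeding go through the outcome or bleeding pages. They are followed past drug stop and analysed as time to event under ITT.
- **Follow-up that varies for both arms.** Staggered entry, event-driven length and early stopping act alike on both arms under concurrent 1:1 randomisation. They create no between-arm bias.
- **Events that cause a stop.** More stops driven by adverse events raise the row for events causing discontinuation, so the downward direction does not hold there.

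Three further arguments do not remove the point. Treatment duration and Kaplan-Meier plots of time to last dose are reported by arm (SAP 6.1.1, 6.1.6). They would reveal an imbalance in exposure but would not correct the percentages. Table layouts sit in a separate specification, but it cannot be assumed to supply a measure that the SAP does not name. Rates rest on a roughly constant hazard, but in the front-loaded example they were still closer to the truth than the crude ratio.

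**Conclusion.** The concern holds in a limited, conditional form. SAP 6.4.1 gives only crude percentages for events whose observation time depends on time on drug. With equal stops the crude ratio is 1.00. At equal true rates it is about 0.95 if one arm stops at 1.5 times the planned rate and about 0.91 at 2 times. At 10 per 100 patient-years that is 0.8 and 1.5 percentage points.

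These sizes rest on assumed adverse-event rates, assumed stop multiples, the planned follow-up of 1 to 3 years rather than the shorter actual course, and stops unrelated to adverse-event risk.

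A reader might go further and conclude that rivaroxaban will look safer than it is. The documents do not support that: they give one stop rate for the whole trial, and the principal safety comparison, bleeding, does not depend on these tables. The change is worth making because by-arm percentages shape the tolerability reading even when untested. It does not affect the trial's main conclusions.

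**What to change.** In SAP 6.4.1, keep the crude counts and percentages and add by arm:

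1. Patient-years at risk, from first dose to the earliest of first event, end of the adverse-event reporting window after the last dose, or last contact.
2. The incidence rate per 100 patient-years for any treatment-emergent event, any serious treatment-emergent event, and events causing discontinuation.
3. A descriptive rate ratio with 95% CI for any serious treatment-emergent event.

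State that the rates assume a roughly constant hazard and that a small distortion remains if events are front-loaded. Define treatment-emergent in days after the last dose, so that numerator and person-time use the same window. At present the on-treatment scope in SAP 4.5.2 runs 2 days and Protocol 7.5.3.2 runs 1 month.

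In Protocol 4.1 and SAP section 3, limit the sentence on time to first event to efficacy and bleeding outcomes.

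The cost is table programming. First-dose, last-dose and last-contact dates are already defined in SAP 4.5.1. The downside is a few extra columns and the constant-hazard caveat.

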4.2 Justification of the design

The target patient population comprises patients with a recent ESUS. These patients have substantial risk for recurrent stroke and other thromboembolic events despite antiplatelet therapy, the current standard of care. A double-blind, randomized trial design comparing rivaroxaban with ASA is deemed the most appropriate design to allow for an unbiased evaluation of rivaroxaban as a treatment option for this patient population in an international trial.

4.3 End of study

For each participating EU country, the end of the study according to the EU Clinical Trial Directive will be reached when the last visit of the last patient for all centers in the respective country has occurred. However, as the primary efficacy outcome of this study is event-driven and requires adjudication by an ICAC, the end of the study as a whole will only be reached when the final efficacy outcome event has been adjudicated for patients from all participating clinical sites (EU and non-EU).

5. Study population – amended

This Phase III, multi-national, study will be conducted in approximately 30 countries¹¹ worldwide in approximately 7000 patients recruited primarily from hospital-based stroke units. Patients who will be enrolled in this study must meet all of the inclusion criteria and none of the exclusion criteria listed in Section 5.1.

5.1 Eligibility

5.1.1 Inclusion criteria - amended

1. Embolic stroke of undetermined source (ESUS) defined as:

- Recent ischemic stroke (including TIA with positive neuroimaging) visualized by brain CT or MRI that is not lacunar (i.e., lacunar infarcts are subcortical infarcts ≤ 1.5 cm in the territory of middle cerebral artery or pons; infarcts involving the cerebellum or lateral medulla are not considered as lacunar infarcts). Patients with multiple simultaneous acute lacunar infarcts on DWI imaging may be included. In case of embolic large artery occlusions clearly documented on angiography who undergo successful recanalization, visualization of infarct on neuroimaging is not mandated¹², and
- Absence of cervical carotid atherosclerotic stenosis (or vertebral and basilar artery atherosclerotic stenosis in case of posterior circulation stroke), that is $> 50\%$, or occlusion in arteries supplying the area of ischemia in CT or magnetic resonance (MR) angiography or conventional angiography or ultrasound, and¹³

¹¹ Was 25 to 30 countries prior to global Protocol Amendment 5.

¹² Text was revised with global Protocol Amendment 5. See Section 13.1 for details.

¹³ Bulleted text was revised with global Protocol Amendment 5. See Section 13.1 for details.

- No history of AF, no documented AF on 12-lead electrocardiogram (ECG) or episode of AF lasting 6 minutes or longer detected after ≥ 24 -hour cardiac rhythm monitoring (Holter or telemetry; at least 20 hours acceptable¹⁴), and
 - No intra-cardiac thrombus on either transesophageal or transthoracic echocardiography¹⁵, and
 - No other specific cause of stroke identified by routine clinical care (e.g., arteritis, dissection, migraine/vasospasm, drug abuse)
2. Time from recent ischemic stroke to randomization and first study medication intake (and only if the investigator regards it as safe to initiate therapy with an anticoagulant) between 7 days and 6 months except:
 - in case of minor strokes (NIHSS ≤ 3), study medication may be initiated as early as 3 days after stroke onset.
 - in case of intravenous thrombolysis treatment or hemorrhagic transformation seen on the qualifying CT or MRI, study medication will not be initiated before 10 days after the acute stroke event unless a repeat CT or MRI scan performed before randomization documents the absence of new or extension of hemorrhage.
 3. All planned diagnostic tests for stroke evaluation must be completed. Brain imaging and 24-hour cardiac monitoring must be repeated if new symptoms of stroke/TIA occurred after the initial stroke evaluation, as does 24-hour cardiac monitoring if symptoms suggestive of AF occur.
 4. Age ≥ 50 years ¹⁶
 5. For patients with age 50-59 years at least one of the following risk factors: stroke or TIA prior to index stroke (includes covert/silent strokes on neuroimaging), diabetes, hypertension, current tobacco smoker, or heart failure.¹⁷
 6. Written informed consent consistent with local regulations governing research in human subjects

5.1.2 Exclusion criteria - amended

1. Severely disabling stroke (modified Rankin score ≥ 4 at screening)
2. If imaging of intracranial arteries is performed by CT or MR angiography or transcranial Doppler: $> 50\%$ luminal stenosis or occlusion in arteries supplying the area of ischemia¹⁸
3. Patent foramen ovale with plans for closure
4. Known serious infection or inflammatory disease that may be the cause of stroke

¹⁴ Global Protocol Amendment 5 added the allowance of monitoring for at least 20 hours to reflect routine practice.

¹⁵ Transesophageal was added with global Protocol Amendment 5.

¹⁶ Prior to global Protocol Amendment 5, patients were eligible for inclusion if they were ≥ 18 years of age (or > 18 years based on country). See Section 13.1.1 for additional details.

¹⁷ This criterion was revised with global Protocol Amendment 5. See Section 13.1 for details.

¹⁸ Prior to global Protocol Amendment 5, luminal stenosis or occlusion was $\geq 50\%$. See Section 13.1 for details.

5. Patient has or is intended to receive an implantable ECG loop recorder
6. Indication for chronic anticoagulation based on guideline recommendations or investigator's judgment; e.g., patient with prosthetic mechanical valve, venous thromboembolism, hypercoagulable state
7. Indication for chronic antiplatelet therapy based on investigator's judgment, in which anticoagulation is not a reasonable substitute, or chronic therapy with a conventional non-steroid anti-inflammatory drug (NSAID) for a non-stroke indication
8. Hypersensitivity or any other contraindication listed in the local labeling for ASA or rivaroxaban
9. Active bleeding, major bleeding within last 6 months, high risk for serious bleeding contraindicating anticoagulant or antiplatelet therapy or history of primary intracranial hemorrhage¹⁹
10. Hepatic disease associated with coagulopathy (prothrombin time prolonged beyond the normal range) and clinically relevant bleeding risk including cirrhotic patients with Child Pugh B and C
11. Estimated glomerular filtration rate (eGFR) < 30 mL/min/1.73 m² as assessed at local laboratory within 1 month of screening
12. Life expectancy less than 6 months
13. Concomitant use of strong inhibitors of both cytochrome P450 isoenzyme 3A4 (CYP3A4) and P-glycoprotein (P-gp), i.e., human immunodeficiency virus protease inhibitors and the following azole-antimycotics agents: ketoconazole, itraconazole, voriconazole, or posaconazole, if used systemically
14. Female of childbearing potential who are not surgically sterile, or, if sexually active not willing to use adequate contraceptive measures with a failure rate less than 1% per year (e.g., prescription oral contraceptives, contraceptive injections, intrauterine device, double-barrier method, male partner sterilization) before entry and throughout the study, as well as pregnant or breast feeding women
15. Inability to cooperate with the study procedures
16. Previous randomization to this study or participation in a study with an investigational drug or medical device within 30 days prior to randomization
17. Close affiliation with the investigational site; e.g. a close relative of the investigator, dependent person (e.g., employee or student of the investigational site)

